7.3 On-Study Evaluations

Please refer to Table 3 located in section 7.1.

7.4 End of Treatment/Off Therapy Measurements (within 30 days post-last dose)

Subjects will be treated until progression of disease, study drug intolerance that is not resolved or amendable to dose reduction, or subject desires to go off study.

Interim history and physical examination, including vital signs and performance status Review of concomitant medications

Laboratory studies:

- CBC with differential count
- Comprehensive metabolic panel
- Magnesium
- CA 19-9

7.5 Follow up/Survival

Please refer to Table 4 located in Section 7.1.

For the purpose of this study, subjects will be seen in follow-up at least every three months until one year after the completion of study treatment. Follow-up evaluations may consist of the interim medical history, physical examination, imaging, CBC, or comprehensive metabolic panel. Any X-rays, CT or MRI scans, or other studies (such as PET scans, bone scans, biopsies, etc.) will be done as clinically indicated and up to the discretion of the treating physician.

After this one-year follow-up period is over, subjects will be continued to be followed for survival until death, withdrawal, or lost to follow up. If subjects are lost to follow-up, every effort will be made at least quarterly to attempt to locate that subject and to determine their health status.

For subjects that come off protocol for reasons other than progressive disease, then CT or MRI scans will be performed every 8 weeks to document disease progression. until disease progression is shown or another anti-cancer therapy is initiated.

8 CRITERIA FOR DISEASE EVALUATION

Tumor response will be assessed using RECIST 1.1ⁱ criteria.

8.1 Tumor Measurement Using RECIST 1.1 Criteria

Measurable disease: the presence of at least one measurable lesion. If the measurable disease is restricted to a solitary lesion, its neoplastic nature should be confirmed by cytology/histology.

Measurable lesions: lesions that can be accurately measured in at least one dimension (the longest diameter), and with a minimum size of 10 mm by CT scan, or 10 mm by caliper measurement during clinical exam, or 20 mm by chest X-ray.

- A malignant lymph node may be considered pathologically enlarged and measurable if it is ≥ 15 mm in short axis by CT scan.
- A lytic or mixed blastic-lytic bone lesion, with identifiable soft tissue component which is evaluable by CT or MRI, may be considered as measurable lesion if the soft tissue component meets the criteria for measurable lesions.
- Cystic metastases may be considered as measurable lesions if they meet the criteria for measurable lesions, however, non-cystic lesions, if present, are preferred as target lesions.
- Tumor lesions in an area previously subjected to loco-regional treatment, may be considered measurable if there has been demonstrated progression.

Non-measurable lesions: all other lesions, including simple cysts, small lesions (longest diameter < 10 mm or pathological lymph nodes with ≥ 10 to < 15 mm short axis) and other truly non-measurable lesions. These include: leptomeningeal disease; ascites; pleural/pericardial effusion; inflammatory breast disease; lymphangitis cutis/pulmonis; abdominal masses that are not measurable by reproducible imaging techniques; blastic bone lesions.

All measurements should be recorded in metric notation, using a ruler or calipers. All baseline evaluations should be performed as close as possible to the treatment start and never more than 4 weeks before the beginning of the treatment.

The same method of assessment and the same technique should be used to characterize each identified and reported lesion at baseline and during follow-up.

Clinical lesions will only be considered measurable when they are superficial (e.g., skin nodules, palpable lymph nodes), and ≥ 10 mm diameter using calipers. For the case of skin lesions, documentation by color photography including a ruler to estimate the size of the lesions is recommended. Whenever possible, imaging evaluation should be preferred over clinical exam.

Chest CT is preferred over chest X-ray, particularly when progression is an important endpoint. The measurability of lesion by CT scan is based on the assumption that CT slice thickness is ≤ 5 mm.

8.2 Baseline Documentation of Target and Non-target Lesions

When more than one measurable lesion is present at baseline, all lesions up to a maximum of five lesions total (and a maximum of two lesions per organ) representative of all involved organs should be identified as target lesions and recorded and measured at baseline.

Target lesions should be selected on the basis of their size (lesions with the longer diameter) and their suitability for accurate repetitive measurements (either by imaging techniques or clinically).

A sum of the diameters (longest for non-nodal lesions, short axis for nodal lesions) for all target lesions will be calculated and reported as the baseline sum diameters. The baseline sum diameters will be used as reference to further characterize any objective tumor regression in the measurable dimension of the disease.

All other lesions (or sites of disease) including pathological lymph nodes should be identified as non-target lesions and should also be recorded at baseline. Measurements are not required and these lesions should be followed as 'present' 'absent', or in rare cases 'unequivocal progression'. Multiple non-target lesions involving the same organ may be recorded as a single item.

8.3 Response Criteria

Evaluation of target lesions

Complete Response (CR): disappearance of all target lesions. Any pathological lymph nodes must have reduction in short axis to < 10 mm.

Partial Response (PR): at least a 30% decrease in the sum of diameters of the target lesions taking as reference the baseline sum diameters.

Progression (PD): at least a 20% increase in the sum of diameters of the target lesions taking as reference the smallest sum on study, and an absolute increase of at least 5 mm. The appearance of one or more new lesions is also considered progression.

Stable Disease (SD): neither sufficient shrinkage to qualify for PR nor sufficient increase to qualify for PD taking as references the smallest sum diameters while on the study.

Evaluation of non-target lesions

Complete Response (CR): disappearance of all non-target lesions and normalization of tumor marker level. All lymph nodes must be non-pathological (< 10 mm short axis).

Non-complete response (non-CR)/non-progression (non-PD): persistence of one or more non-target lesion(s) or/and maintenance of tumor marker level above the normal limits.

Progressive disease (PD): unequivocal appearance of one or more new malignant lesions. Unequivocal progression of existing non-target lesions. Although a clear progression of nontarget lesions only is exceptional, in such circumstances, the opinion of the treating physician should prevail and the progression status should be confirmed later on by a review panel (or study chair/primary investigator).

Evaluation of best overall response

The best overall response is the best response recorded from the start of the treatment until disease progression/recurrence (taking as reference for progressive disease the smallest measurements recorded since the treatment started). In general, the subject's best response assignment will depend on the achievement of both measurement and confirmation criteria.

Table 5 provides a summary of the overall response status calculation at each time point for patients who have measurable disease at baseline. When subjects have non-measurable (therefore non-target) disease only, Table 6 should be used.

| Target Lesion | Non-target Lesions | New Lesions | Overall Response |
|----------------------|--------------------------------|-------------|---------------------|
| CR | CR | No | CR |
| CR | Non-CR/non-PD | No | PR |
| PR | Non-PD or not at all evaluate | No | PR |
| SD | Non-PD or not at all evaluated | No | SD |
| Not at all evaluated | Non-PD | No | Inevaluable |
| PD | Any | Yes or No | PD |

Table 5. Evaluation of Best Overall Response: Subjects with Target Disease, with or without Non-target Disease

| Target Lesion | Non-target Lesions | New Lesions | Overall Response |
|---------------|--------------------|-------------|---------------------|
| Any | PD | Yes or No | PD |
| Any | Any | Yes | PD |

Table 5. Evaluation of Best Overall Response: Subjects with Target Disease, with or without Non-target Disease

Table 6. Evaluation of Best Overall Response: Subjects with Non-target Disease Only

| Non-target Lesions | New Lesions | Overall Response |
|--------------------|-------------|-----------------------------|
| CR | No | CR |
| Non-CR/ non-PD | No | Non-CR/ non-PD ^a |
| Not all evaluated | No | Inevaluable |
| Unequivocal PD | Yes or No | PD |
| Any | Yes | PD |

^a'Non-CR/non-PD' is preferred over 'stable disease' for non-target disease since SD is increasingly used as endpoint for assessment of efficacy in some trials so to assign this category when no lesions can be measured is not advised.

When nodal disease is included in the sum of target lesions and the nodes decrease to 'normal' size (<10 mm), they may still have a measurement reported on scans. This measurement should be recorded even though the nodes are normal in order not to overstate progression should it be based on increase in size of the nodes.

Subjects with a global deterioration of health status requiring discontinuation of treatment without objective evidence of disease progression at that time should be reported as "symptomatic deterioration." Every effort should be made to document the objective progression even after discontinuation of treatment.

In some circumstances, it may be difficult to distinguish residual disease from normal tissue. When the evaluation of complete response depends upon this determination, it is recommended that the residual lesion be investigated (fine needle aspirate/biopsy) before confirming the complete response status. FDG-PET may be used to upgrade a response to a CR in a manner similar to a biopsy in cases where a residual radiographic abnormality is thought to represent fibrosis or scarring.

For equivocal findings of progression (e.g. very small and uncertain new lesions; cystic changes or necrosis in existing lesions), treatment may continue until the next scheduled assessment. If at the next scheduled assessment, progression is confirmed, the date of progression should be the earlier date when progression was suspected.

8.4 Confirmation

In non-randomized trials where response is the primary endpoint, confirmation of PR or CR must be confirmed by repeat measurements that should be performed no less than 4 weeks after the criteria for response are first met. In this trial, as overall response rate is a secondary endpoint, confirmation of response in the form of a PR or CR will occur 8 weeks after the criteria for response are first met, since restaging imaging per the protocol will be performed every other chemotherapy cycle (ie every 8 weeks).

In randomized trials or studies where the primary endpoints are stable disease or progression, confirmation of response is not required. Elimination of the requirement for response confirmation may increase the importance of central review to protect against bias, particularly in studies which are not blinded.

In the case of SD, follow-up measurements must have met the SD criteria at least once after study entry at a minimum interval of 6-8 weeks.

9 STUDY DRUG INFORMATION

- 9.1 Study Drug Name TAS-102 (Lonsurf[®])
 - 9.1.1 Drug Supply TAIHO Oncology, Inc.
 - 9.1.2 Contraindications: none
 - 9.1.3 Special Warnings and Precautions for Use

Myelosuppression

In Study 1, LONSURF[®] caused severe and life-threatening myelosuppression (Grade 3-4) consisting of anemia (18%), neutropenia (38%), thrombocytopenia (5%) and febrile neutropenia (3.8%). One patient (0.2%) died due to neutropenic infection. In Study 1, 9.4% of LONSURF[®]-treated patients received granulocyte-colony stimulating factors.

Obtain complete blood counts prior to and on Day 15 of each cycle of LONSURF[®] and more frequently as clinically indicated. Withhold LONSURF[®] for febrile neutropenia, Grade 4 neutropenia, or platelets less than 50,000/mm³. Upon recovery, resume LONSURF[®] at a reduced dose.

Embryo-Fetal Toxicity

Based on animal studies and its mechanism of action, LONSURF[®] can cause fetal harm when administered to a pregnant woman. Trifluridine/tipiracil caused embryo-fetal lethality and embryo-fetal toxicity in pregnant rats when orally administered during gestation at dose levels resulting in exposures lower than those achieved at the recommended dose of 35 mg/m² twice daily.

Advise pregnant women of the potential risk to the fetus. Advise females of reproductive potential to use effective contraception during treatment with LONSURF[®].

9.1.4 Adverse Event Profile

| Table 7. Per Patient Incidence of Adverse Drug Reactions (≥5%) in Study 1** Occur | ring |
|---|------|
| More Commonly (>2%) than in Patients Receiving Placebo | _ |

| Adverse Reactions | | LONSURF® | | Placebo | | |
|--|-------------|------------------|------------|---------|------------|--|
| | | (N=533) | | (N=265) | | |
| All Grades | Grades 3 | 3-4 | All Grades | | Grades 3-4 | |
| Gastrointestinal | disorders | | | | | |
| Nausea | 48% | 2% | 24% | | 1% | |
| Diarrhea | 32% | 3% | 12% | | <1% | |
| Vomiting | 28% | 2% | 14% | | <1% | |
| Abdominal | 21% | 2% | 18% | | 4% | |
| pain | | | | | | |
| Stomatitis | 8% | <1% | 6% | | 0% | |
| General disorde | rs and adm | inistration site | conditions | | | |
| Asthenia/fatigu | 52% | 7% | 35% | | 9% | |
| e | | | | | | |
| Pyrexia | 19% | 1% | 14% | | <1% | |
| Metabolism and | nutrition d | lisorders | | | | |
| Decreased | 39% | 4% | 29% | | 5% | |
| appetite | | | | | | |
| Nervous system disorders | | | | | | |
| Dysgeusia | 7% | 0% | 2% | | 0% | |
| Skin and subcutaneous tissue disorders | | | | | | |
| Alopecia | 7% | 0% | 1% | | 0% | |

**Study 1: a randomized (2:1), double-blind, placebo-controlled trial in which 533 patients (median age 63 years; 61% men; 57% White, 35% Asian, 1% Black) with previously treated metastatic colorectal cancer received LONSURF[®] as a single agent at a dose of 35 mg/m²/dose administered twice daily on Days 1 through 5 and Days 8 through 12 of each 28-day cycle. The mean duration of LONSURF[®] therapy was 12.7 weeks

10 ADVERSE EVENTS

10.1 Definitions

10.1.1 Adverse Event

The term "adverse event" includes any sign, symptom, syndrome, or illness that appears or worsens in a subject during the period of observation in the clinical study and that may impair the wellbeing of the subject. The term also covers laboratory findings or results of other diagnostic procedures that are considered to be clinically significant (*e.g.*, that requires unscheduled diagnostic procedures or treatment measures, or result in withdrawal from the study).

The adverse event may be:

- A new illness/condition;
- Worsening of a sign or symptom of the condition under treatment, or of a concomitant illness/condition;
- An effect of the study drug; or
- A combination of 2 or more of these factors.

No causal relationship with the study drug or with the clinical study itself is implied by the use of the term "adverse event."

Surgical procedures themselves are not adverse events; they are therapeutic measures for conditions that require surgery. The condition(s) for which the surgery is required may be an adverse event. Planned surgical measures permitted by the clinical study protocol and the condition(s) leading to these measures are not adverse events.

When a clear diagnosis is available that explains the abnormal objective findings, this diagnosis will be recorded as an adverse event and not the abnormal objective findings (*e.g.*, viral hepatitis will be recorded as the adverse event and not the transaminase elevation). If a definitive diagnosis is not available, then the sign(s) (*e.g.*, clinically significant elevation of transaminase levels) or symptom(s) (*e.g.*, abdominal pain) will be recorded as the adverse event.

Adverse events fall into the categories "serious" and "non-serious."

10.1.2 Serious Adverse Event

A serious adverse event is one that at any dose of the study drug or at any time during the period of observation:

- Results in death
- Is life-threatening (defined as an event in which the subject was at risk of death at the time of the event; it does not refer to an event which hypothetically might have caused death if it were more severe)
- Requires inpatient hospitalization or causes prolongation of existing hospitalization (see note below for exceptions)
- Results in persistent or significant disability/incapacity
- Is a congenital anomaly/birth defect
- Is an important medical event, defined as a medical event that may not be immediately life-threatening or result in death or hospitalization but, based on appropriate medical and scientific judgment, may jeopardize the subject or may require intervention (e.g., medical, surgical) to prevent one of the other serious outcomes listed above. Examples of such events include but are not limited to intensive treatment in an emergency department or at home for allergic bronchospasm; blood dyscrasias or convulsions that do not result in hospitalization. "Medically important" should be marked only if no other serious criteria are met.

An "unexpected SAE" is any SAE for which the nature, specificity or severity is not consistent with the currently known adverse event profile of the investigational agent(s) and not listed in the current TAS-102 Global IB.

NOTE: The following hospitalizations are not considered SAEs in UFHCC clinical studies:

- a visit to the emergency room or other hospital department lasting less than 24 hours that does not result in admission (unless considered an "important medical event" or a life-threatening event)
- elective surgery planned before signing consent
- admissions as per protocol for a planned medical/surgical procedure
- routine health assessment requiring admission for baseline/trending of health status (e.g., routine colonoscopy)
- medical/surgical admission for purpose other than remedying ill health state that was planned before study entry. Appropriate documentation is required in these cases.
- admission encountered for another life circumstance that carries no bearing on health status and requires no medical/surgical intervention (e.g., lack of housing, economic inadequacy, caregiver respite, family circumstances, administrative).

Clarification of the difference in meaning between "severe" and "serious"

The term "severe" is often used to describe the intensity (severity) of a specific event (as in mild, moderate, or severe myocardial infarction); the event itself, however, may be of relatively minor medical significance (such as severe headache). Any grade ≥ 3 adverse event per CTCAE is generally considered severe AE. This is not the same as "serious," which is based on the outcome or action criteria usually associated with events that pose a threat to life or functioning. Seriousness (not severity) serves as a guide for defining regulatory reporting obligations.

10.1.3 Non-Serious Adverse Event

A non-serious adverse event is any adverse event not meeting any of the serious adverse event criteria.

10.2 Period of Observation

Following the subject's written consent to participate in the study, all SAEs must be collected.

Collection of all SAEs must continue for 30 days after the last administration of the investigational product or until the start of new anti-tumor therapy, whichever comes first. If applicable, SAEs must be collected that relate to any later protocol-specified procedure (e.g., a follow-up skin biopsy). The investigator should notify the DISC of any SAE occurring after this time period that is believed to be related to the investigational product or protocol-specified procedure.

The investigator will begin collecting non-serious adverse event (NSAE) information at screening. This NSAE information should also be collected from the start of a placebo lead-in period or other observational period intended to establish a baseline status for the subjects. Treated subjects, including those who were prematurely discontinued from the study, will be followed for any adverse events that occur during the study until 30 days following the last dose of study treatment (i.e., the Follow-up Visit). However, if another course of anti-cancer therapy is initiated prior to the 30-day follow-up period visit, collection of adverse events will no longer be performed, with the exception of events that may be possibly, probably, or definitely related to the investigational agent or are clinically significant.

10.3 Documenting and Reporting of Adverse Events by Investigator

All adverse events must be fully recorded in the subject's case record form.

Documentation must be supported by an entry in the subject's file. A laboratory test abnormality considered clinically relevant, e.g., causing the subject to withdraw from the study, requiring treatment or causing apparent clinical manifestations, or judged relevant by the investigator, should be reported as an adverse event. Each event should be described in detail along with start and stop dates, severity, relationship to investigational product, action taken and outcome.

Every attempt should be made to describe the adverse event in terms of a diagnosis that encompasses the component signs and symptoms. If only nonspecific signs or symptoms are present, then these should be recorded as separate diagnoses on the pages of the case report form.

All subjects who have adverse events, whether considered associated with the use of study drug or not, must be monitored to determine the outcome. The clinical course of the adverse event will be followed according to accepted standards of medical practice, even after the end of the period of observation, until a satisfactory explanation is found or the Principal Investigator considers it medically justifiable to terminate follow-up. Should the adverse event result in death, a full pathologist's report should be supplied, if possible.

10.3.1 Assessment of Causal Relationship of Study Drug

The Investigator will provide an assessment of the potential causal relationship between adverse events and study medication by determining whether or not there is a reasonable possibility that the event was caused by the study medication. The relationship or association of the adverse event to the study medication will be characterized as not related, probably not related, possibly related, probably related, or related:

Not Related: There is not a temporal relationship to the study drug administration or the adverse event is clearly due only to the progression of the underlying disease state, intercurrent illness, concomitant medication, concurrent therapy or other known cause.

Probably Not Related: There is little or no chance that the study drug administration caused the adverse event; the event is most likely due to another competing cause, including intercurrent illness, progression or expression of the disease state, or a reaction to a concomitant medication or concurrent therapy appearing to explain the reported adverse event.

Possibly Related: The association of the adverse event with the study drug administration is unknown; however, the adverse event is not reasonably attributed to any other condition.

Probably Related: When a reasonable temporal relationship exists between the adverse event and the study drug administration; significant symptoms abate upon discontinuation of the study drug and there is a reasonable explanation based on known characteristics of the study drug and there is no clear association with preexisting disease or therapy, intercurrent illness, concurrent therapy or other factor(s).

Related: When the adverse event is a known side effect of the study drug or there is a temporal relationship to the administration of the study drug; or the adverse event reappears upon re-administration of the study drug (rechallenge); or the significant symptoms of the adverse event abate upon discontinuation of the study drug (dechallenge).

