11.2 Safety Analysis

Subjects will be examined and graded each cycle for subjective/objective evidence of developing toxicity according to NCI-CTCAE version 4.03 toxicity criteria. Incidence tables will be generated to summarize incidence of subjects reporting at least one episode of each specific adverse event, incidence of adverse events causing withdrawal, and incidence of serious adverse events. Subjects will have laboratory values assessed prior to and on Day 15 of each cycle.

Adverse event data and corresponding toxicity grades during treatment and during long-term follow-up will be summarized in the form of tables. Incidence tables will be generated to summarize incidence of subjects reporting at least one episode of each specific adverse event, incidence of adverse events causing withdrawal and incidence of serious adverse events. The total number of episodes for each event reported (Frequency Table), the severity and attribution to study therapy of each episode reported (Severity Table and Attribution Table) will also be displayed. Listings of adverse events by subjects will include the time to onset, the duration of each event, the severity of each event, and the relationship of the event to study therapy, whether it was a serious event, and whether it caused withdrawal. Safety data will be summarized for the overall subject group and by dose levels. Dose-toxicity curves will be fitted to the final data to estimate the toxicity rates of each dose levels.

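### The causality scale in section 10.3.1 is not ordered: 'Related' is easier to meet than 'Probably Related' and can overlap with 'Not Related', with no rule for which prevails

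*Combined protocol and SAP*

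**What the plan says.** Section 10.3.1 defines five causality categories, from 'Not Related' to 'Related', under a general instruction to judge whether the drug could reasonably have caused the event.

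- The top category is met if the event is a recognised side effect, "or there is a temporal relationship to the administration of the study drug". Two more alternatives follow, again joined by 'or': recurrence on rechallenge, and abatement after stopping (dechallenge).
- The category below it begins "When a reasonable temporal relationship exists between the adverse event and the study drug administration; significant symptoms abate upon discontinuation of the study drug". It goes on, joined by 'and', to require an explanation from what is known of the drug and no clear association with existing disease, other therapy or other factors.
- 'Possibly Related' requires that no other condition reasonably accounts for the event.
- 'Probably Not Related' covers events most likely due to a competing cause. 'Not Related' covers events with no temporal relationship, or clearly due only to disease progression or another known cause.

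Attribution is then used in the analysis. Under section 11.2, "the severity and attribution to study therapy of each episode reported (Severity Table and Attribution Table) will also be displayed", and the by-subject listings show the relationship for each event. Section 10.2 continues AE collection after new anticancer therapy for events "possibly, probably, or definitely related to the investigational agent" or clinically significant. Table 3 in section 5.4.2 uses treatment-related grade 3 or higher events as one of two triggers.

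**The concern.** A causality scale should become harder to satisfy as it rises. Here the top step has four alternative entrances and no exclusion of other causes, while the step below has several conditions that must all hold. An investigator who follows the text literally can code 'Related' on timing alone.

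The categories also overlap, and the section does not say which one wins. Two investigators could both follow the text and code the same event at opposite ends of the scale.

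Safety and tolerability are secondary objectives (section 2.2), and the trial has one arm, so no concurrent control rate shows how many events come from the disease. The Attribution Table is one of the outputs a reader would use to judge that, and its categories would not mean what their order suggests.

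**Working it through.** The plan gives no figure to reproduce. The check is of the logic of the definitions.

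**Step 1. The two upper categories side by side (section 10.3.1).**

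| Element | 'Related' | 'Probably Related' |
|---|---|---|
| Timing | enough alone | required, and must be reasonable |
| Known side effect / explanation from known drug characteristics | known side effect enough alone | explanation required |
| Abatement on stopping | enough alone | required |
| Rechallenge | enough alone | not mentioned |
| No clear association with another factor | not asked | required |

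**Step 2. Enumerate the possible events.** Describe an event by eight yes/no features: timing (T), known side effect (K), rechallenge (R), abatement (D), pharmacological explanation (X), clear association with another cause (C), most likely due to another cause (M), and clearly due only to another cause (O). For consistency, M implies C, and O implies M and C. That leaves 4 combinations of C, M and O. The other five features are free, giving 2^5 = 32. Total: 32 × 4 = 128 profiles.

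- 'Related' = T or K or R or D. It fails only when all four are absent: 2 (X) × 4 = 8 profiles. So 128 − 8 = 120 meet it.
- 'Probably Related' = T and D and X and not C. K and R are free: 2 × 2 = 4 profiles. All 4 have T, so all 4 also meet 'Related'.
- 'Related' through timing alone (T yes; K, R, D no): 2 (X) × 4 = 8 profiles. None meets 'Probably Related', because D is absent.
- Of those 8, 2 × 3 = 6 have a clear association with another cause. Of the 6, 2 × 2 = 4 also meet 'Probably Not Related', and 2 of those 4 also meet 'Not Related'.

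These are counts of logical profiles, not of events or their frequency. 'Possibly Related' was not enumerated because its condition is a pure judgement.

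**Step 3. Two concrete cases.**

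- A symptom that arises during dosing and is clearly due only to progression meets 'Related' by timing, and 'Not Related' by its cause.
- Section 10.2 starts non-serious AE collection at screening. Nausea is a listed reaction in Table 7. Nausea recorded before the first dose meets 'Related' as a known side effect, and 'Not Related' because there is no temporal relationship.

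**Step 4. Is there a tie-break?** Section 10.3.3, on action taken, tells the investigator to choose one item and gives a worst-case hierarchy. Section 10.3.1 has nothing comparable.

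**Step 5. Test the fix.** Let the new 'Related' be T and D and X and not C, plus (R or K), with K read as an established listed reaction. Of the 4 'Probably Related' profiles, the one with neither R nor K drops out, so 3 meet the new 'Related'. The top category is now strictly inside the one below. Since C is absent and T present in all 3, none meets 'Probably Not Related' or 'Not Related'.

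**The case against.** The strongest reply is that no investigator applies these definitions mechanically. The section opens with a judgement of reasonable possibility, and the two lowest categories direct disease events away from the drug. That stands in part: a sensible investigator may still code correctly. It does not supply a precedence rule, and it does not repair the order of the top two categories.

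Second, the downstream reach is limited, and this stands.

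- Table 3 has an independent trigger for clinically concerning events, and its footnotes leave some events to discretion.
- Withholding for other grade 3 or 4 non-hematologic toxicity in section 6.2 names no attribution.
- SAEs are reported under section 10.4.1 whatever their attribution.
- Collection after new therapy already takes in possibly related and clinically significant events, so an error there would only over-collect.

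Third, a reader might infer a size from Table 7 by dividing placebo by drug rates: nausea 24/48 = 50%, abdominal pain 18/21 = 86%. The documents do not support that as a measure of misattribution. Other rows give much lower ratios (alopecia 1/7 = 14%, diarrhea 12/32 = 38%). The population had colorectal cancer. The table lists adverse drug reactions, which meet 'Related' as known side effects rather than through timing.

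Fourth, a reader might conclude that attribution is the only thing separating drug from disease here, and that the wording removes it. That also goes too far. The incidence tables in 11.2 count events regardless of attribution, the listings give time to onset and duration, and the competing categories remain open to the investigator.

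**Conclusion.** The definition is wrong as written and should be corrected. The top category contains the one below it, and events tied to the drug by timing alone can fall in 'Related' and in an unrelated category at once, with no rule to decide. This can classify background disease events as drug-related in the Attribution Table and listings; the text does not show that it will. The extent depends on how literally investigators read the section and cannot be computed from the documents.

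The effect is confined to attributed safety summaries. No PFS analysis, sample-size figure or error rate uses attribution, and the attribution-blind incidence tables and SAE reporting are untouched. The label 'definitely related' in section 10.2 is a smaller inconsistency: it presumably means the top category, but it is not one of the five.

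The conclusion rests on reading the alternatives in 'Related' as alternatives, which is how they are joined, and on there being no coding guidance elsewhere that sets precedence. None appears in the documents.

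**What to change.** 1. In section 10.3.1, redefine 'Related' as meeting every condition of 'Probably Related' plus at least one further element: positive rechallenge, or an established listed reaction to the drug. Merely joining timing to one of the other limbs would not be enough. A known side effect with timing but no abatement would then be 'Related' without being 'Probably Related'.
2. Add a precedence rule: an event that meets 'Not Related' or 'Probably Not Related' is not coded in a higher category.
3. In section 10.2, replace the 'definitely related' wording with the label used in 10.3.1.

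The cost is one paragraph of protocol text, matching CRF guidance, and fewer events in the top category. In particular, an event for which the drug was never stopped cannot show abatement and so cannot reach the top two categories; that is already so for 'Probably Related'. Nothing here proposes a change to the dose-modification rules.
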